10.4.4 Safety Analyses

AEs and SAEs will be recorded and reported as previously described.

10.4.5 Adherence and Retention Analyses

All participants will complete an RA-administered exit survey interview at the conclusion of the baseline visit (either while still in the ED or hospital, or by phone the following day as needed). The exit survey will assess what interventions the participant has received in the ED that are relevant to opioid OD (e.g. substance use screening, OD education, naloxone kit(s) received, treatment referral/follow-up offered). The exit survey interview will also ensure that SDC arm participants receive, at a minimum, OEND, a list of treatment programs, and a handout with Relay program information. RAs will need to check off boxes in the exit survey indicating that the participant has received these items. Participants will also be asked at follow-up assessments what additional Relay program services they have received in the interval since the last assessment.

We will routinely monitor data on number of potentially eligible patients, reasons for ineligibility, refusals and reasons for refusal, and retention/loss to follow-up at all follow-up assessment time points. These data will be compiled and discussed at weekly meetings between the Project Manager and PI(s).

10.4.6 Baseline Descriptive Statistics

Simple descriptive statistics will be examined for baseline characteristics of study participants, as collected on the baseline study survey. Baseline basic characteristics for Relay and SDC arm participants will be compared using bivariate analyses. We expect approximately equal distributions of baseline characteristics for the two study arms given random assignment. Significant differences in baseline characteristics between groups will be adjusted for in outcome analyses.

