| Statistical Analysis | The primary analysis will use a Poisson generalized linear regression model to evaluate the intervention effect on the total number of opioid-involved OD and substance use-related ED visits. We anticipate the availability of 12 months of follow-up data on all participants, but in the event of death or withdrawal from the study, we will adjust the follow-up time appropriately using an offset term. We will include adjustment for study site, as well as other baseline factors that may be unbalanced across arms. The primary effect measure will be the incidence rate ratio comparing Relay to SDC. Some participants may be routinely high utilizers of the ED, and this may lead to overdispersion of the count outcome; we will use a negative binomial model instead of a Poisson model if warranted. Statistical analysis for other aims are described in the full protocol. |

CONFIDENTIAL

This material is the property of the NYU School of Medicine and NYU Langone Health. Do not disclose or use except as authorized in writing by the study sponsor
Behavioral Intervention Template Version: 11 January 2019

Schematic of Study Design

CONFIDENTIAL

This material is the property of the NYU School of Medicine and NYU Langone Health. Do not disclose or use except as authorized in writing by the study sponsor
Behavioral Intervention Template Version: 11 January 2019

1 Key Roles

Principal Investigator (for NYULH study site and overall study)

[name], MHS
NYU Langone Health
Assistant Professor, Departments of Emergency Medicine and Population Health
[name]
New York, NY 10016
[contact]
[contact]

Other NYULH Investigators

[name], MS (MPI)
Department of Population Health
[name]
New York, NY 10016
[contact]
[contact]

[name] (Sub-I)
NYU Langone Health
Department of Population Health, Division of Biostatistics
[name]
New York, NY 10016
[contact]
[contact]

[name] (Consultant)
Qualitative Researcher
John Jay College of Criminal Justice
[name]
Brooklyn, NY 11205
[contact]
[contact]

[name] (Sub-I)
NYU Silver School of Social Work
Department of Social Work
[name]
New York, NY 10003
[contact]
[contact]

[name] (Sub-I)
NYU Langone Health—Brooklyn
Chief of Service, Department of Emergency Medicine
[name]
Brooklyn, NY 11220
[contact]
[contact]

[name] (Sub-I)
Assistant Chief of Service, Emergency Dept, TH
[name]
New York, NY 10016
[contact]

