10.1 Statistical and Analytical Plans

A detailed statistical and analytical plan will be finalized in consultation with the study biostatistician and determined prior to study outcomes analysis. Preliminary approaches are described below but some details of specific statistical analysis plans may change upon biostatistics consultation and/or as the study progresses; no changes in the analysis plan would change the risk to study participants. For minor statistical plan changes, protocol modification approval will not be sought from the IRB.

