10.4.2 Analysis of the Primary Efficacy Endpoint(s)

The primary endpoint is the number of opioid-related adverse events in the 12 months following the index ED visit. Opioid-related adverse events include: any opioid-involved OD (fatal or nonfatal) or any other substance use-related ED visit. Overdose deaths are tracked using the DOHMH comprehensive database of NYC overdose deaths. Data on OD resulting in ED visits or other substance use related ED visits will be collected from administrative data at 12 months, as identified from visit chief complaint and/or diagnoses. We will collect additional self-reported data on OD using a questionnaire that has been used in prior studies. This questionnaire will be administered at each study visit. Participants will be asked whether the OD did or did not result in an ED visit. We will use this information to calculate an estimated 12 month opioid-related OD event count.

The primary outcome will be ascertained by administrative data abstraction with adjustment using self-report data as described above. Administrative data extraction will be completed by members of the study team who are blinded to participant arm assignment. Results for the primary outcome will be compared for independent data abstraction completed by two members of the study team; disagreements will be resolved either by consensus or by a study PI.

The primary analysis will use a Poisson generalized linear regression model to evaluate the intervention effect on the total number of opioid-related adverse events. We anticipate the availability of 12 months of follow-up data on all participants but, in the event of death or withdrawal from the study, we will adjust the follow-up time appropriately using an offset term. We will include adjustment for study site, as well as other baseline factors that may be unbalanced across arms. The primary effect measure will be the incidence rate ratio comparing Relay to SDC. Some participants may be routinely high utilizers of the ED, and this may lead to overdispersion of the count outcome; we will therefore use a negative binomial model instead of a Poisson model if warranted.

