10.4.8 Additional Sub-Group Analyses

Mediators and moderators. Relay may impact primary and secondary outcomes indirectly, by means of its impact on putative mediators grounded in our conceptual model, including OD knowledge, motivation, social support, peer role modeling, stigma, barriers to services, and access to naloxone. Also, the intervention may not be equally effective for all participants. The following individual factors may modify the relation between the Relay intervention and outcomes: age, gender, race/ethnicity, sexual orientation, marital status, ZIP code, housing status, mental and physical health, substance use history, and criminal justice involvement.[118] Understanding mediators and moderators of the Relay intervention will be critically informative for future efforts to scale up and/or modify the program, or replicate it in other settings. We will examine Relay intervention effect mediation and moderation in structural equations models (SEMs). We will estimate SEMs to measure the degree to which the Relay intervention improves knowledge (OD, naloxone), motivation (naloxone, MOUD, other treatment), social support, peer role models, and access to naloxone kits, as well as the degree to which the intervention reduces stigma and perceived barriers to services. Also estimated will be the impact of these putative mediators on the risk of opioid-related adverse events and other outcomes. Models will be fit that include paths from Relay to mediators and outcomes as well as paths from mediators to outcomes. The magnitude and significance of the direct and indirect effects of Relay will be provided. Bootstrapping methods will be used to derive estimates of mediated (i.e., indirect) effects. Bootstrapping approaches to indirect effect inferences rely on repeated random sampling from the data with replacement (e.g., 10,000 times) and use the resulting sampling variability of the estimate as the basis for an interval estimate. To capture potential effect moderation (regarding both the effects of Relay on mediators and the effects of mediators on outcomes), interaction terms will be included in these SEMs. This approach, described by Preacher, Rucker, and Hayes (2007), allows multiple types of effect moderation including moderation of: 1) effect of Relay on mediator; 2) effect of mediator on outcome; 3) indirect effect of Relay on outcome via mediator; and 4) direct effect of Relay on outcome. The software package Mplus accommodates model constraints to facilitate estimation and testing of complex moderated mediation hypotheses. When significant moderator effects are detected, we will estimate and present direct and indirect effects for specific subgroups defined by the moderating variable (e.g., the indirect effect of Relay on overdose via increases in social support *among males*). In addition to moderated mediation analysis based on the standard SEM approach and products of coefficients, we will employ analysis of causal mechanisms grounded in the potential outcomes framework, using marginal structural models. This approach highlights assumptions needed to identify direct and indirect effects of interest: no unmeasured cofounders of the exposure (Relay) and outcome relation; no unmeasured confounders of the mediator and outcome relation; no unmeasured confounders of the exposure and mediator relation; and no measured or unmeasured confounders of the mediator and outcome relation affected by exposure. Because the Relay intervention is randomly assigned, the key issue for the proposed study is addressing confounding of the relation between mediators and outcomes. Because unmeasured confounding of relations between mediators and outcomes may remain despite attempts to measure and include known confounders in the models, sensitivity analysis will be undertaken to determine how the size of the correlation between error for the mediator model and error for the outcome model impacts inferences for direct and indirect effects. Analyses will be undertaken with Mplus (Version 8) and the medflex package in R.

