10.5 Sample Size

The sample size for this study is 350. Our preliminary data indicate the average number of opioid-related adverse events per year in SDC arm will be in the range of 2-3 events/person; this rate is substantiated in the literature.^{19,50,52,58} We wish to be able to detect a decrease in this number of approximately 25% in the Relay arm, a modest effect size judged to be of public health significance. Using a Poisson regression model for the total number of events, 350 participants provide more than 80% power to detect this difference. Specifically, we have 83% power to detect a decrease in the mean event rate from 2.0 per year in SDC to 1.52 in Relay (an incidence rate ratio (IRR) of 1.32 and a 24% reduction). If average opioid-related adverse events in the SDC arm are lower than anticipated, we still have 80% power to detect a decrease in the mean event rate from 1.75 per year in SDC to 1.32 in Relay (IRR = 1.33; a 25% reduction). All calculations assume a two-sided, 0.05-level test, and conservatively include adjustment for possible overdispersion in the primary outcome (overdispersion parameter = 1.6). While formal power and sample size calculations were based on our primary outcome, given that secondary outcomes are generally more common than our primary outcome (e.g., all-cause ED visits) or are time to events expected not to be rare (e.g., time to opioid-involved OD), we expect to have adequate power for secondary outcome analysis as well.

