10.6 Measures to Minimize Bias

10.6.1 Enrollment/Randomization/Masking Procedures

At the enrollment visit, the RA will use an electronic system (REDCap) to trigger assignment to a treatment arm. Randomization will use a 1:1 ratio and is stratified by site; permuted blocks with variable blocks of size 4 and 6 will be used to maintain balance over time and prevent prediction of assignment by the RA. Upon randomization, the RA will immediately inform the participant of the treatment arm assigned.

While the RA conducting the baseline assessment cannot be blinded to the intervention assignment (since it will occur during the same ED visit as the intervention), whenever possible a different RA will be assigned to conduct follow-up interviews in an attempt to maintain blinding. Blinding may be imperfect since participants may reveal their intervention assignment, including based on their answers to the follow-up assessments. Participants themselves cannot be blinded to the treatment condition due to the nature of the intervention. Study staff conducting the administrative data abstraction for the primary study outcomes will be blinded to the intervention assignment. Study analytic staff are blinded to treatment condition until the conclusion of the trial and finalization of the analytic database.

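### Beyond study site, covariates enter the outcome models only through between-arm imbalance, most naturally read as a significant baseline difference; expected prognosis is not a criterion

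*Combined protocol and SAP*

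**What the plan says.** The Protocol Summary (Statistical Analysis) and section 10.4.2 describe the primary model in the same words: "We will include adjustment for study site, as well as other baseline factors that may be unbalanced across arms". Site is the randomisation stratum (section 10.6.1), so its place in the model is fixed in advance.

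Section 10.4.6 has the arms compared by bivariate tests and then states: "Significant differences in baseline characteristics between groups will be adjusted for in outcome analyses". It gives no significance level. The same section expects the arms to be roughly alike because assignment is random.

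Three other statements bear on the point:

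- Section 10.4.2 expects heterogeneity from frequent ED users. Its response is a switch to a negative binomial model, not a covariate. On the self-reported overdose questionnaire it says: "This questionnaire will be administered at each study visit". Baseline is Visit 1 in section 7.3.1.
- Section 10.4.8 lists "age, gender, race/ethnicity, sexual orientation, marital status, ZIP code, housing status, mental and physical health, substance use history, and criminal justice involvement", but as possible moderators, not as covariates of the primary model.
- Section 10.1 promises more detail: "A detailed statistical and analytical plan will be finalized in consultation with the study biostatistician and determined prior to study outcomes analysis". It calls the present approaches preliminary.

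**The concern.** In a properly randomised trial, a significant baseline difference is a chance event. It shows nothing about whether the variable predicts the outcome. Adjusting a count model improves precision when the covariate is prognostic, whether or not the arms differ on it. A significance trigger selects on the wrong property: it usually leaves a strong predictor out, and it can bring an irrelevant variable in.

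Two things are at stake. The first is precision, in a trial whose planned power is only a little above 80%. The second is that the covariates of the primary model are not known until the trial's own baseline table has been tested.

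**Working it through.** **Inputs.** From section 10.5: N = 350, two-sided 0.05, overdispersion φ₀ = 1.6, rates 2.0 vs 1.52 and 1.75 vs 1.32 per year, stated power 83% and 80%. From section 10.6.1: 1:1 allocation, so 175 per arm. Assumed, because the documents give no value: a 0.05 level for the baseline tests, and baseline covariates that explain 10%, 25% or 50% of the overdispersion.

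**The plan's own figure.** Section 10.5 says "we have 83% power to detect a decrease in the mean event rate from 2.0 per year in SDC to 1.52 in Relay". The two-sided Wald calculation on the log rate ratio is:

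SE = √[φ(1/(175·m₀) + 1/(175·m₁))]; power = Φ(|ln(m₁/m₀)|/SE − 1.96)

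- 2.0 vs 1.52: SE = √[1.6(1/350 + 1/266)] = 0.1029; 0.2744/0.1029 − 1.96 = 0.71; power 76.0%.
- 1.75 vs 1.32: SE = √[1.6(1/306.25 + 1/231)] = 0.1102; 0.2820/0.1102 − 1.96 = 0.60; power 72.5%.

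This does not reproduce 83% and 80%. A formula that uses the null variance for the critical value gives 83.4% and 80.3%, but only if the printed ratios are applied as increases from the site-directed care rate (2.0 to 2.63; 1.75 to 2.32). For the stated decreases that formula gives 80.1% and 77.1%. The mismatch is a separate matter. The Wald figures are used here because they describe the decrease.

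**How often the rule admits a predictor.** Under randomisation each baseline test rejects with probability 0.05, so a given predictor enters in about 5% of trials, or 10% at a 0.10 level. With ten independent covariates, the chance of at least one flag is 1 − 0.95¹⁰ = 40.1%.

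**What a pre-specified predictor could add.** Set φ = 1 + (φ₀ − 1)(1 − share) in the Wald formula:

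| φ₀ | Rates | Unadjusted | 10% | 25% | 50% |
|---|---|---|---|---|---|
| 1.6 | 2.0 vs 1.52 | 76.0% | 77.6% | 80.0% | 84.1% |
| 1.6 | 1.75 vs 1.32 | 72.5% | 74.1% | 76.7% | 81.0% |
| 1.2 | 2.0 vs 1.52 | 86.9% | 87.4% | 88.2% | 89.6% |
| 1.2 | 1.75 vs 1.32 | 84.0% | 84.6% | 85.5% | 87.0% |

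At φ₀ = 1.6 the equivalent sample sizes are 350 × 1.6/φ = 364, 386 and 431.

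**What the rule delivers.** The simulation used 4,000 trials per setting, 175 per arm, a control mean of 2.0, one normal covariate plus gamma frailty, average dispersion 1.6 and selection at 0.05. Negative binomial power at a rate ratio of 0.76 was:

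| Share | Unadjusted | Significance rule | Pre-specified |
|---|---|---|---|
| 10% | 77.5% | 77.6% | 79.1% |
| 25% | 77.4% | 77.8% | 81.0% |
| 50% | 77.8% | 78.6% | 85.1% |

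The covariate entered in 4.4–5.3% of trials. The share of the power gain lost is (81.0 − 77.8)/(81.0 − 77.4) = 89% in the middle row and (85.1 − 78.6)/(85.1 − 77.8) = 89% in the last. In the first row the whole gain is only 1.6 points, so its ratio (94%) is imprecise. Quasi-Poisson results were close.

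**Type I error under the rule.** At a rate ratio of 1 and shares of 10%, 25% and 50%, it was 5.3%, 4.5% and 3.9% (negative binomial) and 5.3%, 4.3% and 3.8% (quasi-Poisson), with Monte Carlo SE 0.3 points. A second simulation, with ten covariates of which one was prognostic, gave 4.3–5.0%. The rule is slightly conservative when the covariate is strong.

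**The case against.** The strongest reply is that the plan is not final and the loss may be trivial. Section 10.1 calls these approaches preliminary and promises a detailed plan. Section 10.6.1 says "Study analytic staff are blinded to treatment condition until the conclusion of the trial and finalization of the analytic database", and outcome abstractors are blinded too. No document gives a prognostic figure for age, sex or overdose history. Every participant has just overdosed, which may narrow the spread in overdose history. If that history cannot be used, the list reduces to site, age and sex, and nothing shows that these explain even 10% of the overdispersion. Section 10.5 also calls its allowance of 1.6 conservative.

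Most of this stands and limits the size of the point. It does not remove it. Section 10.1 does not withdraw the rule, so section 10.4.6 applies unless it is replaced. Blinding makes deliberate steering harder, but the covariate set still depends on the data.

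It is also fair to say that section 10.4.2 contains no significance trigger and section 10.4.6 does not refer to it. The link is an inference. It is the natural one, because section 10.4.6 speaks of outcome analyses in general and offers the only test of imbalance.

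A reader might infer three stronger things that the documents do not support:

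- That the rule inflates type I error. The simulations show about 4–5%, provided the fitted model accounts for overdispersion.
- That the plan forbids prognostic covariates. It does not; it names none and gives no criterion for them.
- That the trial will lose a particular number of power points. The explained shares are assumptions and are not tied to any listed variable.

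**Conclusion.** The point holds as one of precision and pre-specification, not of validity. Apart from site, the plan's only stated covariate criterion is between-arm imbalance, read most naturally as a significant bivariate difference at an unstated level. At an assumed 0.05 level this forgoes nearly all the precision that a prognostic covariate could give.

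How much that is cannot be known from the documents. At overdispersion 1.6 the Wald gain is about 2, 4 and 8 points for assumed shares of 10%, 25% and 50%. At 1.2 it is about 0.5 to 3 points. The change is worth making because it is cheap and section 10.1 already provides the place for it.

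**What to change.** In the detailed plan of section 10.1, fixed before unblinding, replace the significance trigger in section 10.4.6 and the matching imbalance wording in section 10.4.2 and the Protocol Summary. Put in their place a short list chosen for expected prognosis from data already planned: site, age, sex and pre-index overdose history. Include overdose history only if the look-back of the baseline instrument (Attachment G, not visible here) covers the period before the index visit. If it does not, leave that item out of the primary model. Report the arm-plus-site model as a sensitivity analysis.

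Pre-index ED counts would match the heterogeneity described in section 10.4.2 more closely. However, the consent described in section 13.3.2 covers administrative data for the 12 months after enrolment, so they are not proposed.

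The cost is SAP wording, a few degrees of freedom and one check of the instrument. There is one real downside. Under section 7.3.1 participants learn their arm at once, and the baseline assessment is completed before Relay contact only as far as possible. Self-reported history could therefore differ by arm. The present rule carries the same exposure, and the arm-plus-site model gives a check on it.

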10.4.7 Planned Interim Analysis

10.4.7.1 Safety Review

Safety review is described in Section 5.8 Premature Termination or Suspension of Study and Section 8.7 Study Halting Rules. Safety endpoints will be monitored at least biannually, in conjunction with biannual DSMB meetings.

10.4.7.2 Efficacy Review

We do not plan formal interim analyses for efficacy.

CONFIDENTIAL

This material is the property of the NYU School of Medicine and NYU Langone Health. Do not disclose or use except as authorized in writing by the study sponsor
Behavioral Intervention Template Version: 11 January 2019

10.4.8 Additional Sub-Group Analyses

Mediators and moderators. Relay may impact primary and secondary outcomes indirectly, by means of its impact on putative mediators grounded in our conceptual model, including OD knowledge, motivation, social support, peer role modeling, stigma, barriers to services, and access to naloxone. Also, the intervention may not be equally effective for all participants. The following individual factors may modify the relation between the Relay intervention and outcomes: age, gender, race/ethnicity, sexual orientation, marital status, ZIP code, housing status, mental and physical health, substance use history, and criminal justice involvement.[118] Understanding mediators and moderators of the Relay intervention will be critically informative for future efforts to scale up and/or modify the program, or replicate it in other settings. We will examine Relay intervention effect mediation and moderation in structural equations models (SEMs). We will estimate SEMs to measure the degree to which the Relay intervention improves knowledge (OD, naloxone), motivation (naloxone, MOUD, other treatment), social support, peer role models, and access to naloxone kits, as well as the degree to which the intervention reduces stigma and perceived barriers to services. Also estimated will be the impact of these putative mediators on the risk of opioid-related adverse events and other outcomes. Models will be fit that include paths from Relay to mediators and outcomes as well as paths from mediators to outcomes. The magnitude and significance of the direct and indirect effects of Relay will be provided. Bootstrapping methods will be used to derive estimates of mediated (i.e., indirect) effects. Bootstrapping approaches to indirect effect inferences rely on repeated random sampling from the data with replacement (e.g., 10,000 times) and use the resulting sampling variability of the estimate as the basis for an interval estimate. To capture potential effect moderation (regarding both the effects of Relay on mediators and the effects of mediators on outcomes), interaction terms will be included in these SEMs. This approach, described by Preacher, Rucker, and Hayes (2007), allows multiple types of effect moderation including moderation of: 1) effect of Relay on mediator; 2) effect of mediator on outcome; 3) indirect effect of Relay on outcome via mediator; and 4) direct effect of Relay on outcome. The software package Mplus accommodates model constraints to facilitate estimation and testing of complex moderated mediation hypotheses. When significant moderator effects are detected, we will estimate and present direct and indirect effects for specific subgroups defined by the moderating variable (e.g., the indirect effect of Relay on overdose via increases in social support *among males*). In addition to moderated mediation analysis based on the standard SEM approach and products of coefficients, we will employ analysis of causal mechanisms grounded in the potential outcomes framework, using marginal structural models. This approach highlights assumptions needed to identify direct and indirect effects of interest: no unmeasured cofounders of the exposure (Relay) and outcome relation; no unmeasured confounders of the mediator and outcome relation; no unmeasured confounders of the exposure and mediator relation; and no measured or unmeasured confounders of the mediator and outcome relation affected by exposure. Because the Relay intervention is randomly assigned, the key issue for the proposed study is addressing confounding of the relation between mediators and outcomes. Because unmeasured confounding of relations between mediators and outcomes may remain despite attempts to measure and include known confounders in the models, sensitivity analysis will be undertaken to determine how the size of the correlation between error for the mediator model and error for the outcome model impacts inferences for direct and indirect effects. Analyses will be undertaken with Mplus (Version 8) and the medflex package in R.

Finally, we will assess the impact of intervention dose, measured using the number, type (phone or in-person conversation, accompaniment to appointments), and duration of contacts; this information is routinely logged by the Relay peer navigator. We will examine the impact of dose using instrumental variables (IV) regression; this approach can substantially increase the strength of causal inference about a variable (such as dose) not fully under experimenter control. IV regression requires a variable related to a dose, but not correlated with any other determinants of dose. Random assignment to study condition meets these requirements; thus, IV regression illuminates the intervention's effectiveness at different dose levels.

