10.4.9 Multiple Comparison/Multiplicity

Not applicable.

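### Moderator subgroup effects (10.4.8) are presented when a moderator is significant, with no threshold, priority order, exploratory label or multiplicity plan, and power for such interactions is low

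*Combined protocol and SAP*

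**What the plan says.** Section 10.4.8 (Additional Sub-Group Analyses) covers the primary and secondary outcomes.

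- Moderators: "age, gender, race/ethnicity, sexual orientation, marital status, ZIP code, housing status, mental and physical health, substance use history, and criminal justice involvement".
- Mediators: "OD knowledge, motivation, social support, peer role modeling, stigma, barriers to services, and access to naloxone".
- Interaction terms enter the structural equation models so that several kinds of moderation can be examined: "1) effect of Relay on mediator; 2) effect of mediator on outcome; 3) indirect effect of Relay on outcome via mediator", and fourth, the direct effect of Relay on the outcome.
- Reporting rule for subgroups: "When significant moderator effects are detected, we will estimate and present direct and indirect effects for specific subgroups defined by the moderating variable".
- The overall direct and indirect effects of Relay are to be given without any such condition.

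Section 10.4.9 ("Multiple Comparison/Multiplicity") reads "Not applicable". Section 3.2 places Aim 3, on mediators and moderators, among the secondary objectives and names four examples of each. Exploratory endpoints are listed separately in Section 4.2.3. Section 10.1 defers a detailed analysis plan until before the outcome analysis.

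**The concern.** The rule uses significance to decide which subgroup effects are estimated and presented, and nothing in the plan controls or qualifies that selection. Two consequences follow. Some moderators will pass by chance, and more will do so the more of the listed factors are crossed. Where power is low, a real interaction passes mainly when its estimate happens to be large, so the subgroup effects shown overstate the differences.

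This matters because the results are meant to be used. Section 10.4.8 ties the moderator findings to scaling up, changing or replicating the programme, and Section 2.2 says the trial will inform whether Relay is modified, replaced or expanded. A subgroup claim that arose by chance, or is inflated, would feed that decision with the standing of a secondary objective.

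**Working it through.** **Inputs.** From 10.4.8: 10 moderators (11 if mental and physical health are separate) and 7 mediators. From 3.2: 4 moderators and 4 mediators as examples. From 4.2.2: 7 secondary endpoints, so 8 outcomes with the primary. From 10.5: N = 350, 2.0 versus 1.52 events per year, overdispersion 1.6. From 10.6.1: 1:1 allocation, so 175 per arm. For the test level, 10.5 states "All calculations assume a two-sided, 0.05-level test", but that concerns the sample size. No level is given for moderators, so 0.05 is an assumption here.

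**1. The plan's own figure.** The documents give no test count, error rate or power for moderation. The nearest figure is the 83% power for the primary comparison. The Signorini formula for Poisson regression gives

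Φ{[√(350 × 2.0/1.6) × ln(1.316) − 1.96 × √4] / √(2 + 2/1.316)} = Φ(0.97) = 83.4%.

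This matches when the IRR of 1.32 is applied upward from 2.0. For the decrease that the text describes, the same formula gives 80.1% and a Wald test on the log rate ratio gives 76.0%. The Wald standard error is used below:

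SE(main) = √[1.6 × (1/2.0 + 1/1.52)/175] = 0.103, with |ln 0.76| = 0.274.

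**2. Number of terms and chance findings, primary outcome.** Terms = moderators × mediators (Relay to mediator) + moderators × mediators (mediator to outcome) + moderators (direct effect). Moderated indirect effects derive from these and are not counted. The expected number by chance is 0.05 × terms and needs no independence. The chance of at least one is 1 − 0.95^terms and does assume it.

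| Reading | Terms | Expected by chance | At least one |
|---|---|---|---|
| 10 moderators, direct effect only | 10 | 0.5 | 40% |
| Aim 3 examples, 4 × 4 | 16 + 16 + 4 = 36 | 1.8 | 84% |
| All listed factors crossed | 70 + 70 + 10 = 150 | 7.5 | 99.95% |

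Across all 8 outcomes the full crossing gives 70 + 560 + 80 = 710 terms and 35.5 expected. All these counts assume no true moderation on any path.

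**3. Power for a direct-effect interaction on the primary outcome.** SE(interaction) = SE(main)/√[q(1 − q)], where q is the subgroup share. The documents give no standard error for the direct effect net of mediators, so the main-effect value stands in for it. With q = 0.5, SE = 2 × 0.103 = 0.206.

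- Interaction as large as the main effect (ratio of IRRs 0.76): 0.274/0.206 = 1.33, and Φ(1.33 − 1.96) gives about 27%.
- Half that size on the log scale: about 10%.
- Double that size: about 76%.
- Main-effect size with a 33/67 split, the share of women expected in 5.4.1: about 24%.

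**4. What the gate does to estimates.** To reach p < 0.05 with an even split, the estimated log ratio must exceed 1.96 × 0.206 = 0.403 in size, that is, a ratio of IRRs of at most 0.67 or at least 1.50. Both are further from 1 than the planned main effect of 0.76. If the true ratio is 0.76, the mean standardised estimate among those passing in the true direction is 1.33 + φ(0.63)/Φ(−0.63) ≈ 2.57. That is about 2.57/1.33 = 1.9 times the true log effect.

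**The case against.** The strongest reply is that probing a significant interaction is ordinary practice and that the plan is less rigid than it may look. Several parts of this stand.

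- **Full crossing is an inference.** Section 10.4.8 says the approach allows several kinds of moderation. It does not say that every moderator is crossed with every mediator, path and outcome. Hence the range in the table rather than 150 alone.
- **Only is an inference.** A reader might take the rule to mean that non-significant interactions go unreported. The text does not say so, and overall direct and indirect effects are given regardless. What is conditional is the subgroup estimates.
- **Mostly chance does not follow.** A reader might infer that most reported subgroups would be false. The chance share is 0.05(1 − t)/[0.05(1 − t) + t × power], where t is the share of tested moderations that are real. At 27% power it is 78%, 63% or 43% for t = 5%, 10% or 20%, and it passes one half only if t is below about 16%. The documents do not fix t.
- **Several false claims even if Relay works alike in everyone does not follow either.** Of the 150 terms, 70 concern mediator-to-outcome paths, where moderation could be real in that case. For the direct effect the expected number is 0.5.
- **ZIP code.** A reader might suppose that its cells would be too small. The documents give neither the number of ZIP codes nor the coding, so this cannot be shown.
- **The power figures have a narrow scope.** They apply to direct-effect interactions on the primary count, not to the 140 mediator-path terms.

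The remaining argument, that a detailed plan will follow under 10.1, does not remove the point. Section 10.1 promises neither full reporting nor a multiplicity approach, and 10.4.9 has already answered that question in the negative.

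**Conclusion.** The point holds. As written, the plan lets significance at an unstated level decide which subgroup effects are presented for a secondary objective, with no priority order, exploratory label or multiplicity approach. Its size depends on how many of the listed factors are tested: between 0.5 and 7.5 chance findings for the primary outcome, on the assumptions of a 0.05 level and no true moderation. Low power at main-effect size makes exaggeration likely even for real direct-effect moderators. The primary analysis is unaffected. The change should be made while the detailed plan is still open.

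**What to change.** In 10.4.8, replace the significance condition with a commitment to report the interaction estimate and 95% CI for every prespecified moderator, whatever its p-value.

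In 10.4.9, replace the current entry with one of two statements:

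- moderator findings are hypothesis-generating; or
- no moderator is called significant until false-discovery control has been applied in defined families: one for the Relay-to-mediator interactions, and one per outcome for the rest. The first family is needed because those tests belong to no single outcome.

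The cost is a few lines of SAP wording and a longer table. The second option will also yield fewer significant moderators.
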